**Table 2: List of relevant data sources in different countries.**

Finland		
Outcome	Register	Register holder
Ectopic pregnancies	Patient Register (Care Register for Health Care)	National Institute for Health and Welfare (THL)
Spontaneous abortions	Patient Register (Care Register for Health Care) (of previous pregnancies from DPP)	THL
Elective terminations	DPP	THL
Stillbirths with and without foetal defects	DPP	THL
Live births with and without congenital anomaly	DPP	THL

Exposure	DPP National Prescription Register National Reimbursement Register	THL Social Insurance Institution (SII)
MS population	DPP, Patient Register (Care Register for Health Care)	THL
General population	Population Register	Statistics Finland (SF)
Sweden		
Outcome	Register	Register holder
Ectopic pregnancies	Patient Register	National Board of Health and Welfare
Spontaneous abortions	Patient Register	National Board of Health and Welfare
Elective terminations	not recorded in SWE	N/A
Stillbirths with and without foetal defects	MBR	National Board of Health and Welfare
Live births with and without congenital anomaly	MBR	National Board of Health and Welfare
Exposure	Prescribed Drug Register	National Board of Health and Welfare
MS population	Patient Register, MS Register	National Board of Health and Welfare
General population	Population Register	Swedish Tax Agency
Norway		
Outcome	Register	Register holder
Ectopic pregnancies	Patient Register	Norwegian Directorate of Health
Spontaneous abortions	Patient Register (of previous pregnancies in MBR)	Norwegian Directorate of Health Norwegian Institute of Public Health (NIPH)
Elective terminations	MBR	NIPH
Stillbirths with and without foetal defects	MBR	NIPH
Live births with and without congenital anomaly	MBR	NIPH
Exposure	Prescription Register	NIPH
MS population	MS Register	Helse Bergen
General population	Population Register	Statistics Norway

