### **9.3.1.1 MS diagnosis and Exposures**

#### **MS Registers (SWE, NOR)**

Information on MS diagnoses will be obtained from MS registers in SWE and NOR. The Norwegian MS Register was established in 1998 (Myhr et al. 2012). In 2012, the register included information on more than 5000 patients regarding demographics, diagnosis, disease modifying treatment and follow-up, as well as disease activity with clinical scoring and several patient-reported outcome measures. The register includes also information on patients' comorbidity, co-medication, and siblings with MS. During 2007 the registry was expanded to include a biobank for collection of blood samples (DNA and serum).

The Swedish MS Register was officially launched in 2001 and contains data since 1996. Since 2011 the register has been part of the Swedish Neuro Register. The register is a nationwide quality registry for patients diagnosed with MS. Most MS specialists in SWE use the Swedish MS Register to enter information on age at onset and sex as well as clinical parameters, such as disease course, relapses, and treatment. The register dates back to 2002 and contains mostly prospective cases, although some clinics have entered data retrospectively.

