#### **Prescription Registers (FIN, SWE, NOR)**

Information on maternal MSDMD exposure before and during pregnancy will be obtained from the Prescription Registers based on reimbursed drug purchases (information is linked to DPP in FIN). The Prescription Registers contain information on outpatient medication purchases in pharmacies (established FIN 1994, SWE 2005, NOR 2004). Prescription-only medicines are only sold in pharmacies, and dispensing requires a prescription issued by a physician or a dentist in FIN, SWE and NOR. In FIN, the register contains information on all purchased prescribed medicines that are reimbursed by the government. This excludes, for instance, most contraceptives. In SWE and NOR, all prescribed medicines purchased in community pharmacies are included irrespective of reimbursement status. The prescription data in the registers includes patient's ID, the generic name of the drug, ATC code, the brand name, the formulation and package, the amount as the defined daily dose (DDD), the date of purchase, the prescribing practice (primary vs. secondary healthcare), and the prescribing physician's area of specialisation.

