### 9.4 Variables

**Exposures:** Maternal MS and related medication exposure before and during pregnancy are the basis of the exposure status of the study subjects in this study.

Pregnancies are considered unexposed if no MSDMDs of interest have been used within three months (except six months for mitoxantrone and cladribine) prior to LMP or during pregnancy. As the maximum reimbursable amount per purchase is the supply for three months of treatment, a pregnancy is defined as unexposed to MSDMDs if there are no purchases of MSDMDs within six months (except nine months for mitoxantrone and cladribine) prior to LMP or during pregnancy. Otherwise a pregnancy is defined as exposed to MSDMDs. Similarly, a pregnancy is defined as unexposed to IFN- $\beta$  if there have been no purchases of IFN- $\beta$  containing medications within six months prior to LMP or during pregnancy and otherwise a pregnancy is defined as exposed to IFN- $\beta$ .

The following MSDMDs and their ATC codes are included in this study: IFN- $\beta$ -1a (L03AB07), IFN- $\beta$ -1b (L03AB08), Peg IFN- $\beta$ -1-a (L03AB13), human normal immunoglobulin (J06BA02), cyclophosphamide (L01AA01), methotrexate (L01BA01, L04AX03), cladribine (L01BB04), mitoxantrone (L01DB07), alemtuzumab (L01XC04), glatiramer acetate (Copaxone®) (L03AX13), leflunomide (L04AA13), natalizumab (L04AA23), fingolimod (L04AA27), teriflunomide (L04AA31), azathioprine (L04AX01), dimethyl fumarate (N07XX09).

**Table 3: More detailed information on individual MSDMD agents, including information on availability and reimbursement in FIN, SWE and NOR.**

MSDMD agent	ATC code	Reimbursed in FIN in Jan 2015 (yes / no) 	Marketing authorisation date			Administration in hospital only 
			FIN	SWE	NOR	
IFN- $\beta$ natural	L03AB02		no	no	no	
IFN- $\beta$ -1-a	Avonex ®	yes	13.3.1997	13.3.1997	5.7.2002	no
	Rebif ®		4.5.1998	4.5.1998	19.8.2003	no
IFN- $\beta$ -1-b	Betaferon ®	yes	30.11.1995	30.11.1995	1.9.2006	no
	Extavia ®		20.5.2008	20.5.2008	20.5.2008	no
Peg IFN- $\beta$ -1-a	Plegridy ®	yes	18.7.2014	18.7.2014	18.7.2014	no
intravenous immunoglobulin	J06BA02	no	16.10.1991	10.10.1981	9.10.1996	yes
cyclophosphamide	L01AA01	no	4.6.1986	28.4.1959	6.4.1959	injection yes tablet no
methotrexate	L01BA01	yes  / no 	25.2.1981	23.6.1964	14.4.1971	tablet no
	L04AX03					infusion yes injection yes/no 

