cladribine	L01BB04	no	25.9.2000	19.11.1993	14.11.1996	injection no infusion yes
mitoxantrone	L01DB07	no	30.8.1993	29.10.1987	1.8.1988	yes
alemtuzumab	L01XC04	no	12.9.2013	no	no	yes
glatimer acetate (Copaxone ® )	L03AX13	yes	8.3.2004	21.9.2001	24.2.2004	no 
leflunomide	L04AA13	yes	2.9.1999	2.9.1999	5.11.2004	no
natalizumab	L04AA23	no	27.6.2006	27.6.2006	27.6.2006	yes
fingolimod	L04AA27	yes	17.3.2011	17.3.2011	17.3.2011	no
teriflunomide	L04AA31	yes	26.8.2013	26.8.2013	26.8.2013	no
azathioprine	L04AX01	yes	31.1.1968	14.3.1968	9.8.1968	no
dimethyl fumarate	N07XX09	no	30.1.2014	30.1.2014	30.1.2014	no

-  Information on only reimbursed medication can be acquired from the National Prescription Register in Finland.
-  Pre-filled syringes/pens and tablets.
-  Injection and infusion solutions - except Trexan injection solution, which is reimbursed.
-  Information on drug use in hospitals and outpatient clinics are not collected in the Prescription Registers and thus information on exposure to these types of medication is not available.
-  Some of the injections are given in hospital and some can be self-administered at home.
-  Earlier there may have been also products that have been administered in hospital.
-  Sources (accessed on 3.2.2015):  
[http://www.ema.europa.eu/ema/index.jsp?curl=pages/medicines/landing/epar\\_search.jsp&mid=WC0b01ac058001d124](http://www.ema.europa.eu/ema/index.jsp?curl=pages/medicines/landing/epar_search.jsp&mid=WC0b01ac058001d124),  
<http://www.fimea.fi/laaketieto/valmisteyhteenvetot/laakkeet>  
<http://www.lakemedelsverket.se/LMF>  
<http://www.legemiddelverket.no/Legemiddelsoek/>

**Outcome variables:** The primary (P), secondary (S) and exploratory (E) outcomes are presented here according to pregnancy timeline.

Ectopic pregnancies (S) (ICD-10: O00) and spontaneous abortions (S) (ICD-10:O03):

- Information will be obtained from Patient Register (FIN, SWE, NOR) based on hospital visits due to these diagnoses

Elective termination of pregnancy (P) (ICD-10: O04):

- Information will be obtained from the DPP (FIN) and from MBR (NOR), where the abortions are registered from GW 12.
- This information is not available from SWE.

Stillbirth (P):

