- New MS immunomodulatory therapies (e.g. cladribine, mitoxantrone and teriflunomide) can have long-term side effects. The proportion of pregnancies in different study cohorts that are using these treatments with respective treatment duration and duration of unexposed period at LMP will be reported. In addition, two separate sensitivity analyses are to be performed: 1) analysis further adjusting for a variable never vs. ever exposed to cladribine, mitoxantrone or teriflunomide as a covariate and 2) analysis adjusting for the duration of cladribine, mitoxantrone or teriflunomide treatment prior to LMP as a covariate.
- Regarding the identification of cohort 1, exposure to IFN- $\beta$  without exposure to any other MSDMD is based on drug purchase data. It is possible that individuals in this cohort have received other MSDMDs in a hospital. In addition, steroids may be given by infusion in a hospital. To account for this possibility, a sensitivity analysis will be done for primary objective #2 using only those individuals from cohort 1 who are unexposed to the proxy MSDMD/steroid hospital exposure during the pregnancy period. To do this, a proxy for the MSDMD /steroid infusion hospital exposure will be defined for cohort 1, based on diagnoses (ICD-10 codes) and all operations codes (Nomesco classification of surgical procedures (NCSP) based classification) recorded pertaining to any hospital visits during the pregnancy period.
- To investigate if cohort 5 could be a proxy for the severity of disease with impact on the pregnancy outcomes, the descriptive statistics (n, %) will be presented for each pregnancy outcome (i.e. serious pregnancy outcome, elective TOPFA, stillbirth, live birth and MCA) in women with MS exposed to other MSDMDs but not to IFN- $\beta$  or glatiramer acetate (Copaxone®) or dimethyl fumarate (Tecfidera®) before or during pregnancy. The impact of disease severity will be assessed by presenting the prevalence of the outcomes for cohort 5 versus cohort 3.

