## 9.9 Limitations of the research methods

### Exposure information

Information on patient-level data on MSDMD used in hospitals and other institutions is not included in the data from prescription databases in FIN, SWE or NOR (Furu et al 2009). This creates observation gaps and therefore there may be some cases classed as MSDMD unexposed, who are actually treated in hospitals. Some drugs are dispensed only through outpatient clinics (for example, antiretroviral drugs), and some new drug groups including some biological drugs (for example, infliximab) are mainly administered in hospitals, and are therefore not usually included in the prescription databases. Nonetheless, in FIN information on patients who have a special reimbursement for i.e. intramuscular injection, and who want to be injected by a professional instead of themselves, is included in the prescription register as the patient buys the medicine from pharmacy (personal communication with [name], SII on Finland Jan 5, 2015). In similar situation with infusion, the medicine is always obtained from the hospital pharmacy, and therefore information is not included in the Prescription Register.

In FIN, most of the MSDMDs are included in the prescription databases and are included in the study database. In FIN, SWE or NOR, IFN- $\beta$  natural (L03AB02) is not on market. Furthermore, human normal immunoglobulin (J06BA02), cyclophosphamide (L01AA01), some products of methotrexate (L01BA01, L04AX03), cladribine (L01BB04), mitoxantrone (L01DB07), alemtuzumab (L01XC04) and natalizumab (L04AA23) are on market, but they are not under the special reimbursement and are given in hospitals. Information on glatiramer acetate (Copaxone®) (L03AX13) is available since 2004, when the product was approved in EU and in NOR.

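### Cohorts are assigned from pharmacy purchases alone, so hospital-given MS drugs are unseen; the planned check omits cohort 3 and the pre-LMP window, and MS Register treatment data go unused

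*Protocol*

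**What the plan says.** **Source.** Protocol section 9.3.1.1: "Information on maternal MSDMD exposure before and during pregnancy will be obtained from the Prescription Registers". Table 2 agrees. The Swedish exposure source is the "Prescribed Drug Register", and the Norwegian one is the Prescription Register. The MS Registers appear in Table 2 only as sources for the MS population. Section 9.4 also names the MS Register among its sources for chronic diseases.

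**Rule.** Section 9.4 operationalises unexposed as "no purchases of MSDMDs within six months (except nine months for mitoxantrone and cladribine", counted back from LMP, with pregnancy itself included.

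**What the source misses.** Table 3 marks immunoglobulin, mitoxantrone, alemtuzumab and natalizumab as given in hospital only, and cladribine as hospital-given by infusion but not by injection. Footnote 4 says hospital and clinic use is "not collected in the Prescription Registers and thus information on exposure to these types of medication is not available". Section 9.9 (Exposure information) says of a similar list of drugs that they "are on market, but they are not under the special reimbursement and are given in hospitals", and accepts that some women classed as unexposed may in fact be treated in hospital.

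**What the MS Registers hold.** For Norway, section 9.3.1.1 says "the register included information on more than 5000 patients regarding demographics, diagnosis, disease modifying treatment and follow-up". For Sweden it lists "age at onset and sex as well as clinical parameters, such as disease course, relapses, and treatment".

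**Planned checks (section 9.7.6).** One analysis restricts cohort 1 to women without a proxy for hospital-given MSDMDs or steroids, built from diagnosis and procedure codes at visits during pregnancy. Another is an "analysis further adjusting for a variable never vs. ever exposed to cladribine, mitoxantrone or teriflunomide as a covariate", with a companion analysis adjusting for duration of those drugs.

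**The concern.** Cohort 3 is meant to be free of every listed MSDMD, and cohort 1 is meant to be IFN-β only. Neither property can be verified for drugs that never pass through a community pharmacy. The misplaced women may have more active disease, and section 9.9 already says confounding by indication is possible. The cohort 5 versus cohort 3 contrast, which the protocol uses to look at severity, has the same problem: hospital-only drugs cannot place a woman in cohort 5 by purchase.

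The adjustment for long-acting drugs could mislead in the same way. Section 9.7.6 names no source for the ever and duration covariates. If they are built from purchases, a woman given mitoxantrone is coded as never exposed, and the analysis then reassures without testing what it claims to test.

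The matter is one of cohort assignment. Cohort entry is the LMP date (section 9.2.4) and is not in question.

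**Working it through.** **1. Which listed drugs the purchase rule can see (Table 3, footnotes 1 and 4, section 9.3.1.1)**

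| Drug | Visible as a purchase? |
|---|---|
| Mitoxantrone | No, in any country (hospital only) |
| Natalizumab, immunoglobulin | No, in any country (hospital only) |
| Cladribine, infusion | No, in any country |
| Cladribine, injection | Possible in SWE and NOR, where all pharmacy purchases are recorded; not in FIN, where it is not reimbursed |
| Teriflunomide | Yes, but authorised only from 26 August 2013 |

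The nine-month purchase window therefore cannot operate for mitoxantrone or infused cladribine. It can operate for injected cladribine in two countries.

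**2. Which cohorts are affected (section 8, Table 1)**

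- Hospital drug, no IFN-β: belongs in cohort 4, is placed in cohort 3, and is absent from cohort 5 where the drug would qualify.
- Hospital drug plus IFN-β: belongs in cohort 2 only, but is also placed in cohort 1.
- Cohort 4 is defined regardless of other MSDMDs, so its membership is correct.

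**3. The plan's own power figure.** Inputs from section 9.5: p0 = 24/331 = 0.0725, n = 1270 and 294, 80% power, two-sided 5%. With RR 1.72, p1 = 0.1247 and the pooled proportion is 0.0823.

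- Critical difference: 1.96 × √[0.0823 × 0.9177 × (1/1270 + 1/294)] = 0.0349
- SD under the alternative: √[0.0725 × 0.9275/1270 + 0.1247 × 0.8753/294] = 0.0206
- (0.0522 − 0.0349)/0.0206 = 0.84, which is 80% power. The stated 1.72 reproduces.

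**4. Reach of the MS Registers.** Expected pregnancies are SWE 482, NOR 412, total 1671 (section 9.5). Swedish register coverage is about 70% (section 9.3.2.1). Norwegian coverage is not stated; full coverage is assumed because Table 2 gives the MS Register as Norway's only MS-population source.

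- 0.7 × 482 + 412 = 749; 749/1671 = 45%
- Reachable cohort 3: 0.76 × 749 ≈ 570
- Reachable cohort 1: 0.8 × 0.22 × 749 ≈ 132

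If Norway contributed nothing, the reach would be 0.7 × 482/1671 = 20%.

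**5. How many would move.** The hospital-treated share q is not in the documents. Assumed 3-10%: 0.03 × 570 = 17 to 0.10 × 570 = 57. Removing 17 to 57 from cohort 3 leaves 1253 to 1213, and the minimum detectable RR against 294 stays at 1.72. Reclassification costs almost no power.

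**6. Possible bias in cohort 1 versus cohort 3.** Let r be the risk ratio of hospital-treated to truly unexposed women (assumed). With contamination of cohort 3 only, expected RR = true RR/(1 − q + q × r). For a true RR of 1.72:

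| q | r = 0.5 | r = 1.0 | r = 1.5 | r = 2.0 | Power at r = 2.0 |
|---|---|---|---|---|---|
| 3% | 1.75 | 1.72 | 1.69 | 1.67 | 77% |
| 5% | 1.76 | 1.72 | 1.68 | 1.64 | 74% |
| 10% | 1.81 | 1.72 | 1.64 | 1.56 | 67% |

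Contamination of cohort 1 works the other way: it multiplies the expected RR by (1 − q1 + q1 × r), where q1 is the contaminated share of cohort 1. Equal shares with the same r would cancel.

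**7. Repeat in MS-Register women only.** With 132 versus 570 at 7.3%, the same formula gives a minimum detectable RR of about 2.12.

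**The case against.** The protocol does not hide the gap. Footnote 4, section 9.3.2.1 and section 9.9 all state it, and section 9.7.6 offers a proxy. That disclosure stands, but the proxy leaves cohort 3 and the pre-LMP window unexamined, and a named source of treatment data goes unused.

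A reader might infer that section 9.3.1.1 flatly contradicts footnote 4. It does not go that far. The footnote describes what follows from the Prescription Registers, and the register descriptions mention treatment without saying that infusions are recorded with start and stop dates. Swedish entry is by most, not all, MS specialists, and some of it is retrospective. Whether the fields can place exposure relative to LMP cannot be told from the protocol.

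A reader might also infer that the longer window is void for cladribine altogether, or that alemtuzumab is a good example. Table 3 supports neither: injected cladribine can appear as a purchase in SWE and NOR, and alemtuzumab is listed as authorised only in FIN, which has no MS Register in Table 2.

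Replacing the primary classification with a mixed source would create its own problem. Ascertainment would differ by country and, within Sweden, by register membership, and adjusting for country does not correct exposure misclassification. That objection stands, and it limits the remedy to a sensitivity analysis. Section 9.9 also says the study is not powered for subsets of the primary cohorts, which applies to a register-only repeat.

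**Conclusion.** The point holds in a bounded form. Purchases cannot show mitoxantrone, natalizumab, immunoglobulin or infused cladribine, so cohort 3 and cohort 1 can contain women they are defined to exclude. The existing check does not reach cohort 3 or the period before LMP. The adjustment for cladribine, mitoxantrone and teriflunomide cannot capture mitoxantrone if built from purchases.

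The reference in the second primary comparison, cohort 4, keeps its correct membership; that comparison is touched only through cohort 1.

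The size is unknown. The 17-57 reclassified pregnancies rest on an assumed 3-10% share and full Norwegian register coverage. Bias in the RR further requires that the hospital drugs, or the disease activity of the women who receive them, change the outcome risk; with r = 1 there is none, and its direction depends on r and on which cohort is contaminated. The documents do not support a claim that the primary result is materially biased. They do support a low-cost improvement to the sensitivity analyses.

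**What to change.** 1. **Table 2, section 9.4 and section 9.7.6:** request the treatment fields of the Swedish and Norwegian MS Registers and confirm whether records are dated.
2. **Section 9.7.6:** where dated records exist, add a sensitivity analysis of primary objective 2 in which a treatment record inside the protocol's own pre-LMP window, or in pregnancy, counts as exposure when assigning cohorts 1, 3 and 5. Leave the purchase-based primary classification in place.
3. Use the same records for the ever and duration covariates on cladribine, mitoxantrone and teriflunomide. State that purchases cannot capture mitoxantrone.
4. Extend the hospital-visit proxy to cohort 3 and to the pre-LMP window. This also covers Finland. The Norwegian Patient Register starts in 2008 (section 9.3.1.2), so Norwegian pregnancies from 2004 to 2007 stay outside it.
5. **Table 3, footnote 4:** say that the information is not available from the Prescription Registers.
6. If the primary comparison is repeated in MS-Register women only, label it supportive and quote its minimum detectable RR of about 2.12.

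**Cost:** extra variables from registers already in the plan. The cost is lowest before the data permit applications, planned one month after registration (section 6). Reach stays partial, at about 45% of planned pregnancies, and ascertainment will differ by country and, within Sweden, by register membership; the report should say so.

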## 2 Terminology

**Birth** A process resulting in a foetus or a child (one or more,  $\geq 1$ ) of at least 22+0 gestational weeks (GW) ( $\geq 22+0$  GW) or weighing at least 500 grams ( $\geq 500$  g) being born by vaginal delivery or by caesarean section (CS). The process of a child being born alive is always a birth.

**Birth weight adjusted for gestational age** is defined according to the gestational age and sex-specific national standards in each country (FIN: Sankilampi et al. 2013). Average for Gestational Age (AGA) is used as reference outcome in relation to Small for Gestational Age (SGA) and Large for Gestational Age (LGA).

**Defect cases:** Cases where 3 or more minor anomalies were detected in the same child.

**Gestational age at birth** is a measure of the age of a pregnancy at birth where the origin is the first day of the woman's last normal menstrual period. Preterm birth refers to gestational age less than 37 GW.

**Induced abortion / elective termination of pregnancy** is artificially induced termination of pregnancy which does not comply with the definition of a birth and which leads to the death of one or more foetus ( $\geq 1$ ) and in which there is no indication of intrauterine foetal death before the termination.

**Live birth** is birth of a child that, irrespective of the duration of the pregnancy, breathes or shows any other evidence of life, such as beating of the heart, pulsation of the umbilical cord or movement of the voluntary muscles, whether or not the placenta is attached or the umbilical cord has been cut.

**Major congenital anomaly (MCA)** refers to a major congenital / foetal structural anomaly, chromosomal defect, teratoma and congenital hypothyroidism involved in a birth, an elective termination of pregnancy for severe MCA, or in a spontaneous abortion. MCAs do not include hereditary diseases and other diseases not associated with congenital anomalies, dysfunction of organs or tissues, developmental disabilities, congenital infections, isolated minor dysmorphic features, normal variations and common less significant congenital anomalies.

**Pregnancy event** refers to terminations of pregnancy, spontaneous abortions, ectopic pregnancies, stillbirths and live births.

**Serious adverse pregnancy outcome** is defined as a composite endpoint of pregnancy including elective termination of pregnancy due to foetal anomaly (TOPFA), MCA or stillbirth.

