**Spontaneous abortion / miscarriage** refers to spontaneous loss of a pregnancy which does not comply with the definition of a birth or a spontaneous intrauterine death of a foetus, detected by a reliable prenatal diagnostic method, and the associated artificial expulsion of the foetus concerned before 22+0 GW ( $< 22+0$  GW), when the foetus weighs less than 500 grams ( $< 500$  g) according to the International Classification of Diseases, 10th revision (ICD-10) diagnosis O03 (WHO, 2014).

**Stillbirth** is birth of a foetus or a child that shows no evidence of life, but complying with the definition of a birth (22+0 GW or  $\geq 500$  g).

**Pregnancy trimesters** are divided as follows: 1st trimester 0-12 GW, 0-84 days from last menstrual period (LMP), 2nd trimester 13-26 GW, 85-182 days from LMP, 3rd trimester from 27 GW to delivery (approximately 40-42 GW), 183 days from LMP to delivery (approximately 280 days).

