  - iii) women with MS exposed to IFN- $\beta$  regardless of exposure to other MSDMDs (cohort 2) vs. unexposed to any MSDMDs (cohort 3).This objective is subject to available data from each country, as only information on ectopic pregnancies or spontaneous abortions requiring treatment in hospitals is available in the study.
5. To estimate the prevalence of the pregnancy outcomes (i.e. serious adverse pregnancy outcome, elective TOPFA (not possible in SWE), stillbirth, live birth and MCA) in cohorts 1 – 4 stratified by country, year of pregnancy outcome, maternal age at LMP, chronic diseases, exposure to any teratogenic medications including steroids, time since MS diagnosis, duration of MS treatment, gestational age and weight of the newborn as relevant for specific pregnancy outcomes.

**The exploratory objectives** are:

6. To describe the following additional characteristics about pregnancy in cohorts 1 – 4:
  - Mode of delivery (CS/vaginal)
  - Preterm birth
  - Birth weight and LBW
  - Birth height and low birth height (LBH), according to country specific standards (FIN Sankilampi et al. 2013)
  - Birth weight (SGA and LGA), height and head circumference for gestational age (AGA)
  - Sex of the newborn
  - Head circumference and low head circumference (according to country-specific standards (FIN Sankilampi et al. 2013)
  - Apgar score (at 1 and 5 minutes)
  - Defect cases
  
7. To estimate the prevalence of i) congenital malformations in live or stillbirths, ii) ectopic pregnancies, iii) spontaneous abortions, and iv) stillbirths in the general population without MS diagnosis (cohort 6) in FIN, SWE, NOR for each pregnancy outcome separately as available in each country. The observed numbers of pregnancy outcomes in cohort 3, matched for age and country, are compared with the expected numbers through indirect standardisation under the assumption that cohort 3 had experienced the same prevalence as women in the general population without MS diagnosis (cohort 6).

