#### 9.2.1 Inclusion criteria

- Women who have had a pregnancy with a recorded outcome consisting of an induced abortion, spontaneous abortion, ectopic pregnancy, or birth during the study period in FIN, SWE or NOR with the event being documented in the relevant databases.

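### Spontaneous abortion is defined to include foetal death in utero with artificial expulsion, but only ICD-10 O03 is extracted, so losses coded O02.1 (missed abortion) are not captured

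*Protocol*

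**What the plan says.** Section 2 (Terminology) gives spontaneous abortion two limbs. The first is spontaneous loss of a pregnancy that does not meet the definition of a birth. The second is "spontaneous intrauterine death of a foetus, detected by a reliable prenatal diagnostic method, and the associated artificial expulsion of the foetus concerned before 22+0 GW". The entry then ties the whole definition to one code, "ICD-10) diagnosis O03 (WHO, 2014".

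Section 9.4 repeats that code for the outcome variable ("Ectopic pregnancies (S) (ICD-10: O00) and spontaneous abortions (S) (ICD-10:O03") and gives the source: "Information will be obtained from Patient Register (FIN, SWE, NOR) based on hospital visits due to these diagnoses". The codes named there for early pregnancy outcomes are O00, O03 and O04. O02 appears nowhere in the protocol.

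Three other provisions decide what happens to a loss of the second kind:

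- Section 2 limits induced abortion to cases "in which there is no indication of intrauterine foetal death before the termination".
- Section 9.2.1 includes "Women who have had a pregnancy with a recorded outcome consisting of an induced abortion, spontaneous abortion, ectopic pregnancy, or birth during the study period".
- Table 6 (Section 9.7.2) uses all pregnancy events as the denominator for spontaneous abortions and ectopic pregnancies. For the primary composite it uses elective terminations plus births.

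Objective 4 (Section 8) notes that "only information on ectopic pregnancies or spontaneous abortions requiring treatment in hospitals is available in the study". Section 9.9 admits that spontaneous abortions are underestimated and puts this down to losses that never reach a hospital.

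**The concern.** The second limb of the definition describes a missed abortion. ICD-10 gives retained dead foetus its own code, O02.1, outside O03. The definition is therefore wider than the code chosen to carry it out. A register search on O03 will find the first kind of loss and will miss the second wherever the hospital coded it as O02.1.

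The losses at issue are not the ones Section 9.9 describes. A loss with artificial expulsion is likely to be treated in hospital, so its record should lie in the Patient Registers the study already uses. The shortfall is avoidable and is not disclosed.

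At stake are the absolute prevalences and the precision for objective 4, which also covers ectopic pregnancies through the shared denominator, and the spontaneous-abortion and ectopic parts of objective 7. The code is best settled before extraction, because a code left out of the data requests may be hard to recover later.

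**Working it through.** **Step 1: follow one record.** Take a foetal death found on ultrasound at 9 weeks, with evacuation in hospital, coded O02.1.

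- Spontaneous abortion: it meets the Section 2 definition, but Section 9.4 looks for O03, so it is not counted.
- Induced abortion: excluded by Section 2, because foetal death preceded the procedure.
- Ectopic pregnancy or birth: no.
- Inclusion: no recorded outcome of a listed type remains, so the pregnancy does not enter the all-pregnancy-events denominator. The woman may still contribute other pregnancies.

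Every link is in the protocol except one, that such a case carries O02.1. That comes from ICD-10 itself, which the protocol cites but does not reprint.

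**Step 2: reproduce the plan's own figure.** Inputs from Section 9.5: cohort 1 n1 = 294, cohort 3 n0 = 1270, baseline p0 = 24/331 = 0.0725, 80% power, two-sided 5%. With p1 = RR × p0 and pbar = (n1·p1 + n0·p0)/(n1 + n0), solve

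p1 − p0 = 1.960·√[pbar(1 − pbar)(1/n1 + 1/n0)] + 0.842·√[p1(1 − p1)/n1 + p0(1 − p0)/n0].

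At RR = 1.72, p1 = 0.1247 and pbar = 0.0823. The left side is 0.0522 and the right side is 0.0349 + 0.0173 = 0.0522. This agrees with the stated 1.72.

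**Step 3: illustrate the size for spontaneous abortion.** The documents give neither the prevalence p of hospital-treated spontaneous abortion nor the share s coded outside O03, so both are assumptions, with s taken as equal in all cohorts. Missed cases leave numerator and denominator:

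- measured prevalence = p(1 − s)/(1 − p·s)
- pregnancies lost = 1671·p·s
- each cohort shrinks by the factor (1 − p·s)

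Example: p = 10%, s = 25% gives 0.075/0.975 = 7.7%, 1671 × 0.025 = 42 lost, and cohorts of 287 and 1238.

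| p | s | lost of 1671 | measured | minimum detectable RR, cohort 1 vs 3 |
|---|---|---|---|---|
| 10% | 0 | 0 | 10.0% | 1.59 |
| 10% | 10% | 17 | 9.1% | 1.63 |
| 10% | 25% | 42 | 7.7% | 1.70 |
| 10% | 50% | 84 | 5.3% | 1.90 |
| 20% | 0 | 0 | 20.0% | 1.38 |
| 20% | 25% | 84 | 15.8% | 1.46 |
| 20% | 50% | 167 | 11.1% | 1.59 |

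**Step 4: relative risks between cohorts.** With the same s in both cohorts, measured RR = true RR × (1 − p0·s)/(1 − p1·s). For p0 = 10% and a true RR of 1.5 (p1 = 15%), s = 25% gives 1.5 × 0.975/0.9625 = 1.52, and s = 50% gives 1.5 × 0.95/0.925 = 1.54. The distortion is small.

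**Step 5: objective 7.** If the official statistics count these losses and cohort 3 does not, observed over expected for a cohort with the population's true prevalence of 10% is 7.7/10 = 0.77 at s = 25% and 5.3/10 = 0.53 at s = 50%. If the statistics also rest on O03 alone, this bias does not arise.

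**Step 6: primary composite.** Its Table 6 denominator contains no spontaneous abortions, so the 1.72 stands.

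**The case against.** The strongest reply is that the protocol does not contradict itself. Section 2 attaches O03 to both limbs and Section 9.4 uses the same code; only the content of ICD-10, which is not reprinted, separates them. That is true, and a reader should not infer an internal contradiction. But the step needed is the plain meaning of a code in the classification the protocol adopts, not a recalled study result. It can be checked against the national versions in use.

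Several further points stand and limit the finding:

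- A reader might infer that a large part of the miscarriages is discarded. The documents give no share and no prevalence. At an assumed 10% share the minimum detectable RR moves only from 1.59 to 1.63.
- The cohort sizes 294 and 1270 derive from a total whose Swedish and Norwegian inputs are births (Table 5 notes). They are not shown to be the all-pregnancy-events denominator, so the figures in Step 3 are illustrative.
- Section 9.9 says the study is not powered for individual outcomes, and objective 4 is made subject to available data. Loss of power here breaks no promise the protocol makes.
- Section 9.9 already discloses undercounting and expects it, without certainty, to be comparable across cohorts. Its stated reason, non-hospital losses, does not cover this gap, but nothing in the documents suggests that coding differs by exposure.
- Section 7 reports no clear association between IFN-beta and outcomes including spontaneous abortion, and then speaks of a possible increased risk. It does not present miscarriage as an established harm.

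**Conclusion.** The concern holds as a mismatch between definition and code for one secondary outcome. Followed literally, the plan leaves out hospital-treated losses that its own definition counts, both as events and as pregnancies. Objective 4 prevalences would be understated and less precise, and the objective 7 ratio may be biased if the official statistics include these losses.

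The size cannot be fixed from the documents. Under the assumed ranges (true prevalence 10% to 20%, 25% to 50% of losses coded outside O03, equal across cohorts), 42 to 167 of 1671 pregnancies drop out. Measured prevalence falls from 10% to 7.7% to 5.3%, or from 20% to 15.8% to 11.1%.

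Two stronger readings are not supported. The first is that the primary result or its power suffers; Table 6 rules that out. The second is that the exposed-versus-unexposed relative risk for spontaneous abortion is materially biased; that would need coding to differ by exposure, which is not shown.

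**What to change.** In Section 2, Section 9.4 and the data requests to all three Patient Registers, define spontaneous abortion as O03 plus O02.1, after confirming the codes in each country's version of ICD-10. Use the same code set for the population figures in objective 7, or state which codes the official statistics use where they cannot be matched. Report O03 alone as a sensitivity figure.

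Add O02.0 (blighted ovum) only if the definition is widened to cover it, since the present wording requires the death of a foetus. Add a sentence to Section 9.9 separating losses missed because they were never treated in hospital from losses missed through coding.

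The cost is one or two more codes from registers already in use, and a few lines of protocol text.
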